6.4.1.2. Analysis

The change from baseline exploratory efficacy endpoints will be analyzed similarly as the primary efficacy endpoint. The proportion of responders will be analyzed similarly as the secondary efficacy endpoints using a logistic regression model.

In addition, the mean change from baseline in the number of migraine days during each month of the 6 month treatment period after the 1st dose of study drug will be summarized using descriptive statistics and plotted.

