9.5.4.4. Exploratory Efficacy Analysis

For the double-blind period, the continuous exploratory efficacy endpoints period will be analyzed similarly as the primary efficacy endpoint. For the proportions of responders for the double-blind period, a logistic regression model will be used similarly as the secondary efficacy endpoint.

For the open-label period, the exploratory efficacy endpoints will be summarized using descriptive statistics.

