2.4. Sample Size and Power Considerations

In the Phase 2b study for CM (study LBR-101-021), the treatment difference between 675/225/225 mg and placebo in change from baseline in monthly average migraine days was 2.1 days (standard deviation [SD]=5.2 days). In the phase 2b study for EM (study LBR-101-022), the treatment difference between 225 mg monthly dose and placebo in change from baseline in monthly average migraine days was 2.7 days (SD=4.1 days). In the Phase 3 study for CM (study TV48125-CNS-30049), the treatment differences to placebo in change from baseline in monthly average migraine days were 1.7 days and 1.8 days for the quarterly dose and the monthly dose, respectively (SD=5.4 days). In the Phase 3 study for EM (study TV48125-CNS-30050), the treatment differences to placebo in change from baseline in monthly average migraine days were 1.3 days and 1.5 days for the quarterly dose and the monthly dose, respectively (SD=3.4 days). Combining the information above, a treatment difference of 1.8 days is used. Considering the patient population is different from the previous studies, a SD of 6 days is used to account for the complexity and uncertainty of this study.

A sample size of 705 (235 patients per treatment group) evaluable patients completing the study is needed for 90% power to show a 1.8 difference in migraine days (assuming a common SD of 6 days) at an alpha level of 0.05. Assuming a 12% discontinuation rate, 268 patients per treatment group will be randomized in the study.

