6.3.1.2. Analysis

The change from baseline secondary efficacy endpoints will be analyzed similarly as the primary efficacy endpoint. For the proportion of responders, a logistic regression model will be used with the following effects: treatment, gender, region, special group of treatment failure (Yes or No), and migraine classification (ie, CM or EM). The stratification factors (as randomized) will be used in the model. The odds ratios, 95% CIs for odds ratios, and p-values will be presented for each fremanezumab treatment group (monthly dose and quarterly dose).

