6.4. Other Efficacy Endpoints Analysis

The exploratory endpoints for the double-blind period are as follows:

- proportion of patients reaching at least 75% reduction in the monthly average number of migraine days during the 12-week period after the 1st dose of study drug
- proportion of patients reaching total (100%) response (no headache) during the 12-week period after the 1st dose of study drug
- proportion of patients reaching total (100%) response (no headache) for at least one month during the 12-week period after the 1st dose of study drug
- mean change from baseline (28-day run-in period) in the monthly average number of headache hours of at least moderate severity during the 12-week period after the 1st dose of the study drug
- proportion of patients reaching at least 50% reduction in the number of migraine days during the 4-week period after the 1st dose of study drug for whom this level of effect is sustained throughout the 12-week period after the 1st dose of study drug
- proportion of patients reaching at least 75% reduction in the number of migraine days during the 4-week period after the 1st dose of study drug for whom this level of effect is sustained throughout the 12-week period after the 1st dose of study drug
- mean change from baseline (28-day run-in period) in the monthly average number of days with nausea or vomiting during the 12-week period after the 1st dose of study drug

Statistical Analysis Plan

- mean change from baseline (28-day run-in period) in the monthly average number of days with photophobia and phonophobia during the 12-week period after the 1st dose of study drug
- mean change from baseline (28-day run-in period) in the monthly average number of days of use of migraine-specific acute headache medications (triptans and ergot compounds) during the 12-week period after the 1st dose of study drug
- mean change from baseline (28-day run-in period) in the number of migraine days during the 12-week period after the 1st dose of study drug for patients who failed topiramate for migraine in the past
- mean change from baseline (28-day run-in period) in the number of migraine days during the 12-week period after the 1st dose of study drug for patients who failed onabotulinumtoxinA for migraine in the past
- mean change from baseline (28-day run-in period) in the number of migraine days during the 12-week period after the 1st dose of study drug for patients who failed valproic acid for migraine in the past

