6.4.1. Electronic Headache Diary Data

6.4.1.1. Definition

The percent reduction in the monthly average number of migraine days during the 12-week period after the 1st dose of fremanezumab will be calculated by formula (4) in Section 6.1. The patient is considered as a responder reaching 50%, 75% or 100% reduction if his/her percent reduction is 50% or more, 75% or more, or 100% respectively. If a patient is early discontinued from the study, he/she will be counted as a non-responder. Similar definition will be applied to calculate the proportion of patients reaching at least 50%, 75% or 100% reduction in the monthly average number of migraine days during the 12-week period after the 4th dose of fremanezumab. Similar definition will be applied to calculate the proportion of patients reaching at least 50% reduction in the monthly average number of migraine days during the 12-week period after the 1st dose of fremanezumab for the subset of patients who failed 2 to 3 classes of preventive medications and valproic acid for migraine in the past and to calculate the proportion of patients reaching at least 50% in the monthly average number of migraine days during the 12-week period after the 4th dose of fremanezumab for the subset of patients who failed 2 to 3 classes of preventive medications in addition to valproic acid for migraine in the past.

The percent reduction in the monthly average number of migraine days for at least 1 month during the 12-week period after the 1st dose of fremanezumab will be calculated by formula (4) where the postbaseline value will be the number of migraine days prorated to 28 days for months 1, 2, and 3. If the patient has 100% reduction or more for at least 1 month, he/she will be considered a responder for that month during the 12-week period after the 1st dose of fremanezumab. Similar definition will be applied to calculate the percent reduction in the monthly average number of migraine days for at least 1 month during the 12-week period after the 4th dose of fremanezumab.

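### The exploratory 100%-response endpoints go to ordinary logistic regression with no method for sparse cells; if no placebo patient responds, the odds ratio is infinite and a default Wald p-value cannot reject

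*SAP*

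**What the plan says.** SAP 6.4 lists two double-blind 100%-response endpoints among the exploratory endpoints: "proportion of patients reaching total (100%) response (no headache) during the 12-week period after the 1st dose of study drug" and "proportion of patients reaching total (100%) response (no headache) for at least one month during the 12-week period". SAP 6.4.1.2 assigns their analysis: "The proportion of responders will be analyzed similarly as the secondary efficacy endpoints using a logistic regression model". The model referred to is in SAP 6.3.1.2: "a logistic regression model will be used with the following effects: treatment, gender, region, special group of treatment failure (Yes or No"), with migraine classification as the last term. Its output is also fixed there: "The odds ratios, 95% CIs for odds ratios, and p-values will be presented for each fremanezumab treatment group". Protocol 9.5.4.4 plans the same for the double-blind period: "a logistic regression model will be used similarly as the secondary efficacy endpoint". It makes the open-label endpoints descriptive, so the point concerns the double-blind endpoints only.

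For the 12-week responder definition, SAP 6.4.1.1 adds: "If a patient is early discontinued from the study, he/she will be counted as a non-responder".

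Neither document gives an exact, penalised or other method for responder models with few or no events. The only small-cell rule in the SAP is the switch to Fisher's exact test in 5.3, and it covers baseline comparisons. Neither document says whether the logistic p-values are Wald, score or likelihood-ratio, and neither gives an expected 100%-response rate.

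**The concern.** Patients have failed 2 to 4 classes of preventive treatment, and about half should have chronic migraine with at least 15 headache days in the run-in. Twelve weeks of total response is a demanding outcome in such a population, more so on placebo and with early leavers counted as failures. A placebo count of zero is therefore a realistic result for the 12-week endpoint.

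Maximum-likelihood logistic regression breaks down there. With no responders in the reference arm, the estimated log odds ratio for each active arm increases without limit and its standard error increases faster. The report would carry an arbitrary odds ratio, an interval that is in effect unbounded and, under the usual default, a p-value near 1 however many fremanezumab patients responded. The team would then have to print that result or choose another method after seeing the data.

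**Working it through.** **Sample size per arm.** The plan states no power or rate for these endpoints, so the only figure to reproduce is the arm size. With a difference of 1.8, SD 6, two-sided 0.05 and 90% power, n = 2 × (1.960 + 1.282)² × 6² / 1.8² = 233.5, so 234; the SAP has 235 (2.4: "A sample size of 705 (235 patients per treatment group) evaluable patients completing the study is needed for 90% power"). Allowing for 12% discontinuation, 235 / 0.88 = 267.05, so 268 per arm and 804 in all. This agrees with the plan. I use 268, because early leavers stay in the denominator as non-responders.

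**Assumed inputs.** Response rates are my assumptions, shown as a range. Tests are two-sided at a nominal 0.05. One active arm is compared with placebo, without covariates.

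**Chance of no placebo responders**, (1 − p)^268:

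| True placebo rate | 0.1% | 0.25% | 0.5% | 1% | 2% |
|---|---|---|---|---|---|
| P(zero responders) | 76.5% | 51.1% | 26.1% | 6.8% | 0.4% |

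**What a zero does to the Wald test.** With a active and b placebo responders out of n each, log OR = ln[a(n − b) / (b(n − a))] and SE = √[1/a + 1/b + 1/(n − a) + 1/(n − b)]. As b goes to 0, the log OR grows like ln(1/b) and the SE like √(1/b), so their ratio goes to 0 and the test cannot reject. A fit of the planned three-arm model with simulated covariates and no placebo responders shows the same. Between 8 and 25 iterations the log odds ratio for one active arm rose from 6 to 23, its SE from 6 to 29,705 and its Wald p from 0.31 to 0.999.

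With no placebo responders, the smallest active count that rejects is 4 (score), 5 (Firth penalised likelihood ratio) or 6 (Fisher). For Wald there is none.

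**Example, 0/268 v 8/268.** Fisher's exact p = 0.0074. In a 2×2 table Firth's fit adds 0.5 to each cell, so OR = (8.5 × 268.5) / (0.5 × 260.5) = 17.5. The penalised likelihood-ratio statistic is 8.74 (p = 0.003), and the profile 95% interval runs from 2.2 to about 2,270: very wide, but finite and excluding 1.

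**Power and false-positive rate, by enumerating all pairs of binomial counts (%):**

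| Placebo, active | Wald | Firth penalised LR | Fisher | Ordinary LR |
|---|---|---|---|---|
| 0.25%, 3% | 22.8 | 75.5 | 64.4 | 85.7 |
| 0.5%, 3% | 28.5 | 60.2 | 49.0 | 71.0 |
| 1%, 4% | 48.2 | 60.8 | 51.5 | 66.8 |
| 1%, 5% | 70.0 | 80.5 | 73.6 | 83.3 |
| 2%, 5% | 42.7 | 47.2 | 39.3 | 48.6 |
| 2%, 6% | 63.4 | 67.3 | 60.1 | 68.1 |
| 0.5%, 0.5% (no effect) | 0.0 | 0.6 | 0.1 | 8.1 |
| 1%, 1% (no effect) | 0.2 | 2.6 | 1.0 | 9.1 |

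The gain of Firth over Wald is 53, 32, 13, 11, 5 and 4 points in the first six rows. Firth stays below 5% in both no-effect rows. The ordinary likelihood-ratio test does not.

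**The case against.** **The SAP does not prescribe a Wald test.** This stands. The power loss belongs to a software default that I assume, and the likelihood-ratio test from the same fit does reject with no placebo responders. It is a poor rescue, though: with equal rates of 0.5% to 1% it rejects 8% to 9% of the time at a nominal 5%. The infinite odds ratio and unusable Wald interval remain whichever p-value is printed.

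**A reader might infer a loss of some 10 to 50 points wherever placebo response is 1% or less.** The documents give no rates, so no such general range can be drawn from them. The loss depends on the active rate and on the comparator. At 1% placebo with 4% to 5% active it is 11 to 13 points against Firth but only 3 to 4 against Fisher. At that rate the zero count itself can account for at most 6.8 points; the rest is the general conservatism of Wald tests with few events.

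**Rarity is inferred, and better supported for one endpoint than for two.** This also stands. The at-least-one-month endpoint needs one clear month of three, and the paragraph of SAP 6.4.1.1 that defines it does not repeat the rule for early leavers. That section also derives 100% response from migraine days, a looser standard than freedom from headache, and episodic patients can enter with as few as 4 qualifying days.

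**The harm is contained.** SAP 6.1 plans descriptive statistics for all efficacy data, so 0 against 8 would be visible beside the odds ratio. SAP 7 makes no multiplicity adjustment for exploratory analyses, and no confirmatory claim rests on these endpoints.

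**Conclusion.** The point holds as a gap in method for two exploratory endpoints, and it is minor. The planned fit has no finite odds ratio when the placebo arm has no responders. Under the usual default the p-value then cannot show a difference, however large.

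The size rests on three assumptions: 268 per arm, Wald p-values, and response rates that I chose. Within them the power cost against Firth's penalised likelihood-ratio test is about 53 points at 0.25% placebo and 3% active, 32 points at 0.5% and 3%, and 11 points at 1% and 5%. At 2% placebo with 5% to 6% active it falls to 4 or 5 points.

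It would go too far to conclude that the plan mandates a test that cannot work, that zero placebo counts are to be expected on both endpoints, or that any primary or secondary conclusion is at risk. The documents support none of these.

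**What to change.** In SAP 6.4.1.2, before unblinding, state that both double-blind 100%-response endpoints (12-week and at-least-one-month) are analysed with the terms of SAP 6.3.1.2 fitted by Firth penalised likelihood, with profile penalised-likelihood 95% intervals and p-values from the penalised likelihood-ratio test, whatever the observed counts.

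Two details matter:

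- **Name the p-value.** A Wald p-value read from the Firth fit gives back much of the gain: about 51% power instead of 75.5% at 0.25% placebo and 3% active. The programming specification should say how the penalised likelihood-ratio p-value is obtained, because asking for profile limits on the odds ratio does not in itself supply it.
- **Do not switch method on counts by arm.** If a trigger is wanted for other responder endpoints, base it on the pooled, blinded responder count.

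The cost is one sentence, an option in the fitting procedure and a small programming step for the p-value. The drawback is slight shrinkage of the odds ratio.

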6.4.2. Six-Item Headache Impact Test

6.4.2.1. Definition

Migraine related disability will be assessed using the HIT-6 ([Appendix C](#)). The questionnaire measures the adverse impact of headache on social functioning, role functioning, vitality, cognitive functioning, and psychological distress. It also assesses headache severity. Each question is answered on the scale ranging with the following response options: 6 points (never), 8 points (rarely), 10 points (sometimes), 11 points (very often), and 13 points (always). The total score is obtained from summation of the 6 question points. The HIT-6 total score ranges between 36 and 78, with larger scores reflecting greater impact. If 1 or more items are missing then the total score is missing.

6.4.2.2. Analysis

The change from baseline values after the 3rd dose of study drug in the HIT-6 total scores will be analyzed using the same ANCOVA method as described in Section 6.2.2 and MMRM method as described in Section 6.2.3.1.

6.4.3. Migraine Disability Assessment

6.4.3.1. Definition

The MIDAS questionnaire ([Appendix D](#)) is a 5-item instrument developed to assess headache-related disability based on lost days of activity in 3 domains (work, household work, and nonwork) over the previous 3 months. The total of the scores of the first 5 questions is used for grading of disability, with scores of 0 to 5, 6 to 10, 11 to 20, and ≥ 21 interpreted as disability grades 1 (little or no disability), 2 (mild disability), 3 (moderate disability), and 4 (severe disability), respectively.

6.4.3.2. Analysis

The change from baseline after the 3rd dose of study drug in the MIDAS total scores will be analyzed using the same ANCOVA method as described in Section 6.2.2 and MMRM method as described in Section 6.2.3.1.

6.4.4. Migraine-Specific Quality of Life

6.4.4.1. Definition

The 14-item MSQOL questionnaire ([Appendix E](#)) is designed to measure how migraines affect and/or limit daily functioning across 3 domains: Role Function-Restrictive domain comprising 7 items assessing how migraines limit one's daily social and work-related activities; Role Function-Preventive domain comprising 4 items assessing how migraines prevent these activities, and Emotional Function domain comprising 3 items assessing the emotions associated with migraines. Raw dimension scores are computed as a sum of item response and rescaled to a 0 to 100 scale such that higher scores indicate better quality of life. [Appendix F](#) provides the scoring instructions on how to rescale the raw score to the scales that will be used for the analysis.

6.4.4.2. Analysis

The transformed scores for the 3 domains (ie, Role Function-Restrictive, Role Function-Preventive, and Emotional Function) of MSQOL will be derived. The change from baseline after the 3rd dose of study drug in the MSQOL domains will be analyzed using the same ANCOVA method as described in Section 6.2.2 and MMRM method as described in Section 6.2.3.1.

6.4.5. EuroQol-5 Dimension Questionnaire

6.4.5.1. Definition

The EQ-5D-5L ([Appendix G](#)) is a standardized questionnaire that assesses overall state of health. The EQ-5D-5L consists of 2 parts. In Part 1, patients rate their health state in 5 domains: mobility, self-care, usual activities, pain/discomfort, and mood, using a scale of 1 to 5 where 1=no problems, 2=slight problems, 3=moderate problems, 4=severe problems, and 5=extreme problems. In Part 2, patients rate their health state on a 100 mm visual analog scale; a rating of 0 represents the worst imaginable health state, and a rating of 100 represents the best imaginable health state.

6.4.5.2. Analysis

The number and percentages of patients rating their scale of 1 to 5 for the 5 domains will be presented. The change from baseline values after the 3rd dose of study drug on the visual analogue scale will be analyzed using the same ANCOVA method as described in Section [6.2.2](#).

6.4.6. Two-Item Patient Health Questionnaire/9-Item Patient Health Questionnaire

6.4.6.1. Definition

The PHQ ([Appendix H](#)) is a 9-item questionnaire with each item corresponding to 1 criterion of the Diagnostic and Statistical Manual for Mental Disorders 4th edition diagnostic criteria for major depressive disorder. Each of the items is scores on a scale of 0 (“not at all”), 1 (“several days”), 2 (“more than half the days”), and 3 (“nearly every day”) based on the frequency of symptoms during the past 2 weeks ([Sptizer et al 1999](#)). The PHQ-2 was developed from the PHQ-9 to rapidly screen for depression and consisted of the first 2 questions of the PHQ-9. The PHQ-2 and the PHQ-9 are validated measures for detecting and monitoring depression, anxiety, and somatization ([Kroenke et al 2010](#)).

If the PHQ-2 is positive (ie, a score of ≥ 3), patients will complete questions 3 through 9 (unique questions) of the PHQ-9.

6.4.6.2. Analysis

The change from baseline in the total PHQ-9 score will be analyzed using the same ANCOVA method as described in Section [6.2.2](#).

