^a All visit 2/baseline procedures must be performed before study drug administration and health care resource utilization inquiry. Inquiries about adverse events will be made before and after study drug administration. Post-dose inquiries will be made before the patient leaves the study center.

^b Collection of prior medications is limited to those medications administered within 6 months before study drug administration (visit 2) and preventive medications taken within 10 years.

^c Height will be measured only at the screening visit.

^d Electrocardiograms will be performed in triplicate. Procedure will be performed before other assessments (eg, blood draws and administration of questionnaires). The ECGs should be performed after the patient has been supine for at least 5 minutes.

^e Before pulse and blood pressure are measured, the patient must be in a supine or semi-erect/seated position and resting for at least 5 minutes. The same position and arm should be used each time vital signs are measured for a given patient.

^f Procedures for unscheduled visits.

^g Women of child bearing potential only.

^h Postmenopausal women only.

ⁱ Eligible patients will be given an electronic headache diary device and will be trained in its use and compliance requirements on the day of screening.

^j Patients will complete electronic headache diary entries about the previous day daily beginning on day -27 through the EOT/ early termination visit.

^k Blood samples for plasma drug concentration determination will be collected prior to dosing (as applicable) at visits 2, 3, 4, 5, 6, and 8.

^l Blood samples for serum ADA assessment will be collected prior to dosing (as applicable) at visits 2, 3, 5, 6, 8, and 9 and will also be collected upon observation of any severe hypersensitivity reaction i.e., severe hypersensitivity reaction and anaphylaxis.

^m A single blood sample for pharmacogenomic analysis will be collected at visit 2, before study drug administration from patients who consent to this procedure. A separate informed consent form for pharmacogenomic sampling must be signed by the patient.

ⁿ Patients will respond first to the PHQ-2. They will respond to questions 3 through 9 (unique questions) of the PHQ-9 only if PHQ-2 is positive.

^o The eC-SSRS Baseline/Screening version will be completed at visit 1 and the eC-SSRS Since Last Visit version will be completed at all other visits.

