- perform physical examination, including height and weight
- perform 12-lead ECGs in triplicate
- perform vital signs measurement
- perform beta human chorionic gonadotropin (β -HCG) serum pregnancy test (for women of child-bearing potential)
- perform FSH for postmenopausal women only
- inform patients of study restrictions and compliance requirements
- complete eC-SSRS

Patients who meet all inclusion and none of the exclusion criteria will be given an electronic headache diary device and will be trained in its use and compliance requirements on the day of screening. Patients will complete electronic headache diary entries about the previous day daily beginning on day -27 (visit 1) through the EOT/early withdrawal visit (visit 8).

2. Procedures Before Administration of Investigational Medicinal Products (Baseline Visit 2, Day 0+3 Days)

Patients who meet all inclusion and none of the exclusion criteria at visit 1 will continue to visit 2 (week 0), when baseline assessments will be conducted.

The following procedures will be performed at visit 2:

- review inclusion and exclusion criteria
- assign randomization/treatment numbers and enter in CRF
- perform clinical laboratory tests (serum chemistry, hematology and coagulation, urinalysis)

- perform physical examination, including weight
- perform 12-lead ECGs in triplicate
- perform vital signs measurements
- perform urine pregnancy test (women of child bearing potential only)
- review study compliance
- review electronic headache diary
- obtain blood samples for plasma concentration of IMP prior to dosing
- obtain a blood sample for serum ADA assay prior to dosing
- obtain blood collection for serum, plasma, and RNA biomarker analysis
- obtain urine sample for biomarker analysis
- collect a saliva sample for biomarker analysis
- obtain blood samples for pharmacogenetics before study drug administration from patients who consent to this procedure
- complete HIT-6
- complete the MIDAS
- complete the PHQ-2/ PHQ-9. Patients will respond first to the PHQ-2. Patients will respond to questions 3 through 9 (unique questions) of the PHQ-9 only if PHQ-2 is positive.
- complete the MSQOL questionnaire
- complete the EQ-5D-5L questionnaire
- complete the WPAI questionnaire
- inquire about adverse events and health care resource utilization
- inquire about concomitant medication

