- mean change from baseline (28-day run-in period) in the number of migraine days during the 12-week period after the 1st dose of study drug for patients who failed topiramate for migraine in the past
- mean change from baseline (28-day run-in period) in the number of migraine days during the 12-week period after the 1st dose of study drug for patients who failed onabotulinumtoxinA for migraine in the past
- mean change from baseline (28-day run-in period) in the number of migraine days during the 12-week period after the 1st dose of study drug for patients who failed valproic acid for migraine in the past
- mean change from baseline (28-day run-in period) in the number of migraine days during the 12-week period after the 1st dose of study drug for the subset of patients who failed 2 to 3 classes of preventive medications and valproic acid for migraine in the past

Statistical Analysis Plan

- proportion of patients reaching at least 50% reduction in the monthly average number of migraine days during the 12-week period after the 1st dose of fremanezumab for the subset of patients who failed 2 to 3 classes of preventive medications and valproic acid for migraine in the past
- mean change from baseline (day 0) in disability score, as measured by the 6-item Headache Impact Test (HIT-6), at 4 weeks after administration of the 3rd dose of study drug
- mean change from baseline (day 0) in disability score, as measured by the Migraine Disability Assessment (MIDAS) questionnaire, at 4 weeks after the administration of the 3rd dose of study drug
- mean change from baseline (day 0) in quality of life, as measured by the Migraine-Specific Quality of Life (MSQOL) questionnaire, at 4 weeks after administration of the 3rd dose of study drug
- mean change from baseline (day 0) in the health status, as measured by the EuroQol-5 Dimension (EQ-5D-5L) questionnaire at 4 weeks after administration of the 3rd dose of study drug
- mean change from baseline (day 0) in patient depression status, as measured by the 2 item Patient Health Questionnaire (PHQ-2) and 9-item Patient Health Questionnaire (PHQ-9), at 4 weeks after administration of the 3rd dose of study drug
- mean change from baseline (day 0) in patient work productivity and activity impairment, as measured by the Work Productivity and Activity Impairment (WPAI) questionnaire, at 4 weeks after administration of the 3rd dose of study drug

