6.4.7. Work Productivity and Activity Impairment Questionnaire

6.4.7.1. Definition

The generic version of the WPAI questionnaire ([Appendix I](#)) measures the overall effect of health on productivity at work and daily activities. The specific health problems version of the WPAI questionnaire allows investigators to attribute productivity and activity impairment issues to specific health conditions. After the employment status of a respondent is identified, 3 open-ended questions are asked concerning (1) hours absent from work due to health problems (or specific condition), (2) hours absent from work due to other reasons, and (3) hours actually worked. Two additional questions are included that ask about the impact of health on

Statistical Analysis Plan

productivity, 1 concerning productivity at work and the other concerning daily activities outside of work. The response format of each item of the WPAI questionnaire consists of an 11-point scale ranging from 0 (no impairment) to 10 (complete impairment) (Reilly et al 1993).

The following scores will be derived based on the WPAI:GH questionnaire. Multiply scores by 100 to express in percentages.

- percent work item missed due to health: $\frac{Q2}{Q2+Q4}$
- percent impairment while working due to health: $\frac{Q5}{10}$
- percent overall work impairment due to health: $\frac{Q2}{Q2+Q4} + \left[\left(1 - \frac{Q2}{Q2+Q4} \right) \times \frac{Q5}{10} \right]$
- percent activity impairment due to health: $\frac{Q6}{10}$

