6.4.7.2. Analysis

For the patients who are currently employed, their scores of

- percent work item missed due to health
- percent impairment while working due to health
- percent overall work impairment due to health
- percent activity impairment due to health

will be analyzed using the same ANCOVA method as described in Section 6.2.2.

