17. CHANGES TO ANALYSES SPECIFIED IN THE STUDY PROTOCOL

The planned interim analyses (see Section 2.5.1) have been updated to indicate that there will be 2 interim database locks and a final database lock. This was updated as clarification.

The PP analysis set definition (see Section 3.4) has been modified to update “completing the study” to “completing the double-blind treatment period”. This change has been made as this analysis set is only used for the primary and secondary efficacy endpoints which are for the double-blind treatment period only. Additional details have also been added regarding compliance and incorrect study drug administered. A statement has also been added to clarify that a blinded data review meeting will be conducted prior to the interim database lock to determine the exclusion of the patients.

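### SAP 6.4.7.2 limits the WPAI activity score to employed patients although the question concerns life outside work; SAP 6.4.6.2 names no model for the listed PHQ-2 endpoint

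*SAP*

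**What the plan says.** **WPAI.** SAP 1.2 lists as an exploratory endpoint the "mean change from baseline (day 0) in patient work productivity and activity impairment" at 4 weeks after the 3rd dose. SAP 6.4.7.1 describes two questions on the impact of health, "1 concerning productivity at work and the other concerning daily activities outside of work". It derives four scores:

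- work time missed, from Q2 and Q4
- impairment while working, from Q5
- overall work impairment, from Q2, Q4 and Q5
- activity impairment, as Q6/10

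SAP 6.4.7.2 introduces all four with "For the patients who are currently employed, their scores of" and sends them to the primary-type ANCOVA. No analysis of Q6 is given for patients who are not employed. SAP Section 17 records the interim locks and that "The PP analysis set definition (see Section 3.4) has been modified", but says nothing about WPAI.

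**PHQ.** SAP 6.4.6.1 says that if PHQ-2 is positive (3 or more), "patients will complete questions 3 through 9 (unique questions) of the PHQ-9". Protocol Table 2, footnote n, makes the condition explicit: "They will respond to questions 3 through 9 (unique questions) of the PHQ-9 only if PHQ-2 is positive". Protocol Appendix B repeats it separately for visit 2 (day 0) and visit 5 (week 12). SAP 1.2 names both PHQ-2 and PHQ-9 as the depression measures. The analysis in SAP 6.4.6.2 is one sentence: "The change from baseline in the total PHQ-9 score will be analyzed using the same ANCOVA" method.

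**The concern.** The employment restriction makes sense for the three work scores, which cannot be formed or interpreted without a job. It has no such basis for Q6, which concerns activities outside work and has no term for hours worked. Answers from patients not in work would be collected and then left out, at a cost in precision and in coverage of the trial population.

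For the PHQ, a visit with PHQ-2 below 3 leaves seven of the nine items unasked by design. The planned ANCOVA needs a nine-item total at both day 0 and week 12, so the analyst has to know how such visits are scored. PHQ-2 is asked of every patient at both visits and is a listed endpoint, but the PHQ analysis section names no model for it.

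**Working it through.** **Arm size.** SAP 2.4 gives a difference of 1.8 days, SD 6, two-sided alpha 0.05 and power 90%. Then n = 2 × (1.960 + 1.282)² × 6² / 1.8² = 2 × 10.51 × 11.11 ≈ 233.5, or 234 per arm. The plan states 235, which has power 0.902; 235/0.88 rounds up to the stated 268. The figure reproduces. It is used below only as a convenient arm size. The mITT set may be larger, but the ratios do not depend on it.

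**Q6.** Let u be the share not employed, with the same SD in both groups. Patients left out per arm = 235 × u. SE ratio, employed only against all respondents = 1/√(1 − u).

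| u (assumed) | left out per arm | SE ratio | SE increase |
|---|---|---|---|
| 20% | 47 | 1/√0.8 = 1.118 | 12% |
| 30% | about 70 | 1/√0.7 = 1.195 | 20% |
| 40% | 94 | 1/√0.6 = 1.291 | 29% |

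**PHQ ranges.** Items are scored 0 to 3.

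- PHQ-2-negative visit: observed score 0 to 2; the seven unasked items could add 0 to 7 × 3 = 21; the full total therefore lies anywhere from 0 to 23.
- PHQ-2-positive visit: full total 3 to 27, all observed.

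A nine-item change is fully observed only if both visits are positive, so the number cannot exceed the number positive at baseline.

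For scale, assume 10%, 20% or 30% positive at each visit, a bivariate normal score, between-visit correlation 0.4, 0.6 or 0.8, and no drug effect. None of these values is in the documents. The share positive at both visits is then:

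| positive per visit | r = 0.4 | r = 0.6 | r = 0.8 |
|---|---|---|---|
| 10% | 2.7% | 3.9% | 5.6% |
| 20% | 7.6% | 9.9% | 12.9% |
| 30% | 14.2% | 17.3% | 21.1% |

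Per arm this runs from 235 × 0.027 ≈ 6 to 235 × 0.211 ≈ 50 patients.

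**Where a PHQ rule might stand.** SAP 4.3 gives missing-item rules for HIT-6 and points to Appendix F for MSQOL. It has none for the PHQ. The content of Appendix H, the PHQ form, is not shown.

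**The case against.** **WPAI.** The comparison among employed patients is a fair randomised comparison, and the endpoint is exploratory. The endpoint wording in SAP 1.2 is not decisive: it does not limit the work scores to the employed either, and no one disputes that restriction. The silence of Section 17 also proves little, because Protocol 6.1.7 defines no derived scores and the SAP introduction allows the SAP more detail. All of this stands. The point rests instead on what Q6 asks and how it is computed.

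**PHQ.** A reader might infer that the plan has no scoring rule for PHQ-2-negative visits. The documents do not support that: Appendix H is not shown, and this SAP does put scoring rules in appendices. A reader might also infer that PHQ-2 has been dropped. It has not. It is listed as an endpoint (SAP 1.2 and 6.4) and as a day 0 baseline value (SAP 4.2), SAP 6.1 promises descriptive statistics for all efficacy data, and Protocol 9.5.4.4 provides a primary-type analysis for continuous exploratory endpoints in general. What remains is that SAP 6.4.6.2 names a model for PHQ-9 only.

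A third tempting reading is that PHQ-2 would be the more powerful measure and should replace PHQ-9 as the main depression analysis. That ordering holds if the drug shifts all nine items equally. It can reverse if items 3 to 9 respond more than items 1 and 2. The documents support neither pattern, so no ranking is made.

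**Conclusion.** The Q6 restriction is an avoidable loss, not a bias. Its size is a standard error about 12% to 29% larger if 20% to 40% of patients are not employed. That rests on an assumed employment rate, on equal SD, and on patients without a job answering Q6. The visible text does not exempt them, but Appendix I is not shown. Treating the comparison among the employed as valid takes employment status as of day 0; the SAP does not name the visit.

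The PHQ part is a clarification. A fully observed nine-item change exists only for patients positive at both visits, and a named endpoint lacks a named model. The shares shown above are illustrations under assumed rates.

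Both endpoints are exploratory and carry no multiplicity control. Sample size and the primary and secondary conclusions are untouched, and no false-positive risk is shown. This is an optional improvement.

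**What to change.** - **SAP 6.4.7.2:** analyse activity impairment (Q6) in all double-blind mITT patients with data. Keep the employment restriction for the three work scores only.
- **SAP 6.4.6.2:** add an ANCOVA of PHQ-2 change from day 0 to 4 weeks after the 3rd dose, in all double-blind mITT patients with data and with baseline PHQ-2 as covariate, alongside the PHQ-9 analysis. Confirm the PHQ-9 scoring rule for PHQ-2-negative visits, or cite Appendix H if it holds one. Report by arm the number with a fully observed PHQ-9 change.
- **SAP Section 17:** record the Q6 population and the PHQ addition.

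The cost is two SAP paragraphs and one Section 17 entry. Endpoint lists and data collection do not change. The amendment should be approved before the first interim database lock, as SAP 2.5.2 already requires of any SAP amendment.
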